8.5.8.3 Withdrawal/Discontinuation during any Retreatment Period

If a subject is withdrawn from the study for any reason during a Retreatment Period, the investigator should make every effort to perform the assessments scheduled for the Retreatment Week 26 Visit. In addition, investigators should contact these subjects by telephone approximately 30 days after the Retreatment Week 26 Visit (ie, the End of Retreatment Period Visit) to collect follow-up safety information.

8.5.8.4 Withdrawal/Discontinuation during the Follow-up Period

If a subject is withdrawn from the study for any reason during the Follow-up Period, the investigator should make every effort to perform the assessments scheduled for the Month 48 Visit.

9 Adverse Events

9.1 Definitions

9.1.1 Adverse Event

As per the ICH guidelines, an AE is any untoward medical occurrence in a patient or clinical investigation subject administered a pharmaceutical product and which does not necessarily have a causal relationship with this treatment. An AE can, therefore, be any unfavorable and unintended sign (including an abnormal, clinically significant laboratory finding), symptom, or disease temporally associated with the use of a medicinal product (eg, the investigational product), whether or not considered related to the medicinal product (eg, the investigational product).

The period of observation for AEs extends from the time the subject gives informed consent until 30 days after the last administration of any investigational product (see [Section 9.4](#) for further details).

Adverse events may include:

- A clinical event occurring after written informed consent but before administration of the investigational product.
- Exacerbation (ie, an increase in the frequency or severity) of a pre-existing condition. Illness present before study entry should be recorded in the medical history section of the eCRF and only be reported as an AE if there is an increase in the frequency or severity of the condition during the study.
- Intercurrent illnesses with an onset after administration of investigational product.

Adverse events do not include:

- Events identified at Screening that meet exclusion criteria.
- Medical or surgical procedures (the condition that leads to the procedure is the AE).
- Situations where an untoward medical occurrence has not taken place, including:
 - Planned hospitalizations due to pre-existing conditions, which have not worsened.
 - Hospitalizations that occur for procedures not due to an AE (eg, cosmetic surgery).
 - Hospitalizations for a diagnostic procedure where the hospital stay is less than 24 hours in duration or for normal management procedures (eg, chemotherapy).

- Overdose of investigational product or any concomitant therapy that does not result in any adverse signs or symptoms.
- Selected endpoints and transplant-related disease events, including:
 - Elevated creatinine.
 - Worsening of renal function and related laboratory changes.
 - Hospitalization for per protocol IVIg administration or other immune suppressive therapy.
 - Hospitalization for per protocol plasmapheresis.
 - Allograft failure.

For laboratory safety parameters, any instances of absolute values being outside the reference range or changes at any visit after study start that are considered by the investigator as clinically significant must be recorded in the eCRF as AEs. In addition, at the investigator's discretion, any changes or trends over time in laboratory parameters can be recorded in the eCRF as AEs if such changes or trends are considered to be clinically relevant, even if the absolute values are within the reference range.

Laboratory findings do not need to be reported as AEs in the following cases:

- Laboratory parameters already beyond the reference range at Screening, unless a further increase/decrease can be considered an exacerbation of a pre-existing condition.
- Abnormal laboratory parameters caused by mechanical or physical influences on the blood sample (eg, in vitro hemolysis) and flagged as such by the laboratory in the laboratory report.
- Abnormal parameters that are obviously biologically implausible (eg, values that are incompatible with life or outside the measuring range).
- An abnormal laboratory value that cannot be confirmed after repeat analysis, preferably in the same laboratory (ie, the previous result could be marked as not valid and should not necessarily be reported as an AE).

9.1.2 Adverse Event of Special Interest

There are several AEs that will be monitored as AEs of special interest to enable an adequate risk-benefit evaluation of the C1-INH.

The following events will be considered AEs of special interest:

- Thromboembolic events (TEEs).
 - Any systemic TEE is considered an SAE and should be reported as such. Additionally, any non-systemic TEE (eg, a TEE associated with dialysis access or other vascular access) that meets the serious criteria must be reported as an SAE.
 - Any non-serious access-related thrombosis should be entered as an AE on the eCRF and will be part of the regular review of AEs of special interest by the IDMC.
- Anaphylaxis.
 - All events of anaphylaxis are considered SAEs and should be reported as such.

9.1.3 Serious Adverse Event

An SAE is defined as any untoward medical occurrence that at any dose:

- **Results in death** – The event must be the cause of death for the SAE to meet this serious criterion.
- **Is life-threatening** – The term “life-threatening” refers to an event in which the subject was at risk of death at the time of the event; it does not refer to an event that hypothetically might have caused death if it had been more severe.
- **Requires in-patient hospitalization or prolongation of existing hospitalization** – CSL considers “hospitalization or prolongation of existing hospitalization” for at least 24 hours as the defining criterion for an SAE. Hospital admissions for planned surgery or for normal disease management procedures (eg, chemotherapy) are not considered as defining criteria for SAEs.
- **Results in persistent or significant disability or incapacity.**
- **Is a congenital anomaly or birth defect.**
- **Is medically significant** – A medically significant event is defined as an event that does not necessarily meet any of the SAE criteria, but which is judged by a physician to potentially jeopardize the subject or require medical or surgical intervention to prevent one of the above outcomes listed as an SAE criterion. Transmission of an infectious agent may be considered medically significant.

Additionally, AEs of special interest may be considered SAEs (see [Section 9.1.2](#)).

Adverse events that do not fall into the above categories are defined as non-serious AEs.

9.2 Severity of Adverse Events

The severity of each AE (ie, non-serious and serious AEs) is to be assessed by the investigator as described in Table 15.

Table 15 Severity of Adverse Events

Severity	Definition
Mild	A type of AE that is usually transient and may require only minimal treatment or therapeutic intervention. The event does not generally interfere with usual activities of daily living.
Moderate	A type of AE that is usually alleviated with additional specific therapeutic intervention. The event interferes with usual activities of daily living, causing discomfort but poses no significant or permanent risk of harm to the subject.
Severe	A type of AE that interrupts usual activities of daily living, or significantly affects clinical status, or may require intensive therapeutic intervention.

Source: CDISC SDTM Severity Intensity Scale for Adverse Event Terminology.

9.3 Causality of Adverse Events

The causal relationship of an AE to the investigational product **must always be assessed** by the investigator. All AEs will be classified as either **related** or **not related** to the investigational product. If a causality assessment is not provided for an AE (including an SAE), then that AE will be considered related to the investigational product.

The degree of certainty with which an AE is attributed to the investigational product (ie, C1-INH or placebo) or an alternative cause (eg, natural history of the underlying disease, concomitant therapy) will be determined by how well the event can be understood in terms of:

- Known pharmacology of the investigational product.
- Clinically and/or pathophysiologically plausible context.
- Reaction of a similar nature previously observed with similar products, or reported in the literature for similar products as being product related (eg, headache, facial flushing, pallor).
- Plausibility supported by the temporal relationship (eg, the event being related by time to administration or termination of treatment with the investigational product, drug withdrawal or reproduced on rechallenge).

9.4 Observation Period for Adverse Events

For TP1 and TP2, the observation period for AEs and SAEs reporting for an individual subject will start at the time of giving written informed consent for participation in the current study and finish 30 days after the last administration of any investigational product as a part of TP1 and TP2.

Throughout the Responder Follow-up Period, if the investigator becomes aware of an AE that has started after the observation period has finished, and there is at least a possible causal relationship to the investigational product, the event must be reported to CSL (see Section 9.6).

If a subject participates in a Retreatment Period, the observation period for AEs and SAEs reporting for an individual subject will start at the Retreatment Day 1 Visit and finish 30 days after the last administration of any investigational product as a part of Retreatment Period.

9.5 Follow-up of Adverse Events

Every effort should be made to follow AEs until resolution or stabilization. Ongoing, non-serious AEs that have not resolved or stabilized will be followed until the subject completes the study. Serious adverse events will be followed until the AE resolves, stabilizes, or the subject is lost to follow-up.

9.6 Adverse Event Reporting

9.6.1 Adverse Events

At each clinical evaluation, the investigator (or delegate) will determine whether any AEs have occurred. AEs will be recorded in the AE/SAE eCRF. If known, the medical diagnosis of an AE should be recorded in preference to the listing of individual signs and symptoms. The investigator must follow up on the course of an AE until resolution or stabilization. If an AE is ongoing after the end of study visit, the AE will continue to be followed up until resolution, stabilization, or the subject is lost to follow-up.

If, during the study period, a subject presents with a preexisting condition that was not noted at the time of study entry, the condition should be retrospectively recorded in the Medical History eCRF.

9.6.2 Serious Adverse Event Reporting

This study will comply with all applicable regulatory requirements and adhere to the full requirements of ICH Topic E2A (Clinical Safety Data Management: Definitions and Standards for Expedited Reporting).

For SAEs occurring during the study, the investigator or delegate will enter all relevant information in the eCRF.

An electronic document containing the AE page and other applicable pages of the eCRF must be sent (via facsimile or email) to CSL together with a Notification of Serious Adverse Event at Investigator Site cover page, which has been signed and dated by the Investigator. If an electronic document is not able to be generated (eg, internet access problem), a handwritten paper SAE report must be completed, which must be signed and dated by the investigator.

All SAEs that occur during the course of the study, whether or not causally related to the investigational product, must be entered into the eCRF and CSL notified immediately (within 24 hours of the investigator becoming aware of the event).

Adverse events occurring in the period between the time the subject gave written informed consent and the first exposure to the investigational product that meet 1 or more of the seriousness criteria be entered into the eCRF in the same manner as other SAEs and will be included in the clinical study database.

Any SAE that occurs after the Week 38 Visit or during the Responder Follow-up Period that is considered to be causally related to the investigational product must be reported immediately (ie, within 24 hours of the investigator becoming aware of the event) to CSL.

The minimum reporting requirements for reporting of SAEs include:

- Subject identification number.
- Suspected medicinal product and/or procedure.
- Event term.
- Reporting source identification.

If the minimum requirements for reporting are fulfilled, the investigator should not wait to receive additional information to fully document the event.

In addition, the investigator must:

- Report all SAEs to the relevant Institutional Review Board (IRB)/Independent Ethics Committee (IEC) within the timeframe specified by the IRB/IEC.
- Enter follow-up information in the eCRF until the SAE has resolved, or, in the case of permanent impairment, until stabilized.
- Ensure that the causality assessment for all SAEs is entered in the eCRF.

In cases of death, the investigator should supply CSL and the IEC/IRB (as applicable) with any additional information as it becomes available (eg, autopsy reports and detailed medical reports).

9.6.3 Other Significant Event Reporting

Adverse events of special interest (see [Section 9.1.2](#)) that are considered SAEs should be reported accordingly (see [Section 9.6.2](#))

9.6.4 Overdose

Any overdose that occurs in association with an adverse sign or symptom must be entered into the eCRF as an AE; if the AE meets any seriousness criteria, the event must be reported as an SAE (see [Section 9.6.2](#)).

Details of overdose of the investigational product (defined in [Section 7.5](#)) must be recorded in the study treatment administration eCRF. Details of overdose of any concomitant therapy must be recorded in the Concomitant Medication eCRF.

9.6.5 Pregnancy and Breastfeeding

A female subject or female partner of a male subject who becomes pregnant while participating in the study, or up to and including 30 days after the last dose of the investigational product, must notify the investigator immediately.

If a female subject becomes pregnant, she must discontinue treatment with the investigational product immediately, but may continue other study procedures at the discretion of the investigator. If the female subject is in the active treatment period of the study, her participation will be discontinued and the procedure for discontinuation of a subject will be followed, as described in [Section 4.2](#)).

CSL must be notified within 5 days of the investigator becoming aware of the pregnancy (by entry of appropriate data into the eCRF).

Whenever possible, a pregnancy in a subject or in a female partner of a male subject exposed to the investigational product should be followed to term so as to assess any potential occurrence of congenital anomalies or birth defects. Any follow-up information, including premature termination and the status of the mother and child after delivery, should be reported by the investigator to CSL using a Pregnancy Reporting/Outcome Form.

9.7 IRB/IEC Reporting Requirements

The time frame within which an IRB/IEC must be notified of deaths and investigational product-related unexpected SAEs is stipulated by each IRB/IEC. It is the investigator's responsibility to comply with the requirements for IRB/IEC notification. CSL will provide investigators with all details of all SAEs reported to regulatory authorities.

10 Statistics

10.1 Sample Size Estimation

10.1.1 Sample Size Based on the Primary Efficacy Endpoint

The sample size is based on the primary efficacy endpoint of loss-of-response status (binary endpoint of loss-of-response or not), at the End-of-TP2 (ie, within 25 weeks after randomization). The null hypothesis is that there is no difference between C1-INH and placebo with respect to the proportion of subjects with loss-of-response at the End-of-TP2. Let p_0 and p_1 be the expected proportion of subjects with loss-of-response in TP2 in the placebo and C1-INH treatment groups, respectively. The alternative is that there is a difference between the treatment groups. That is, $H_0: p_0 = p_1$ versus $H_1: p_0 \neq p_1$.

The power procedure in SAS STAT software (Cary, NC SAS Institute Inc.) was used to estimate the sample size, based on the likelihood ratio chi-square test. Determination of the sample size was based on the following assumptions:

- The proportions of subjects experiencing loss-of-response at the End-of-TP2 will be 0.75 with placebo and 0.30 with C1-INH.
- There will be at least 90% power to detect a statistically significant effect with two-sided test with alpha = 0.05.
- Logistic regression model with treatment effect will be used for the primary efficacy analysis. Wald test statistic for treatment effect from Logistic regression has approximately same distribution as chi-square [Fleiss et al, 2003]. Therefore, the sample

size calculation based on chi-square test is used to ensure similar power for hypothesis testing.

- Treatment allocation will be 1:1.
- The planned interim analysis for futility will not impact the type 1 error for the final analysis.

Under these assumptions, a total of 60 subjects (30 randomized to C1-INH and 30 randomized to placebo) will provide approximately 95% power. The study will enroll a sufficient number of subjects to ensure that 60 subjects are randomized.

The assumptions above are based on a prospective single-arm pilot study to investigate the C1-INH added to high-dose IVIG for the treatment of acute AMR non-responsive to conventional therapy [Viglietti et al, 2016a]. A total of 6 subjects received C1-INH and IVIg for 6 months. The primary endpoint was change in eGFR. These were compared to a historical control of 21 subjects who received IVIg. In the prospectively treated C1-INH group, 0/6 subjects experienced decline in eGFR at 6 months (0; 95% confidence interval [CI], 0 to 46%); and 4/6 subjects had a greater than 20% increase in eGFR (67%; 95% CI, 22% to 96%). In the historical control group, 15/21 subjects (71%; 95% CI, 48% to 89%) experienced decline in eGFR during a comparable 6 month period.

10.1.2 Power for Allograft Survival

Allograft survival status (or all-cause allograft failure) at the end of 48 months after enrollment represents clinical confirmation of the effect on the allograft of improving eGFR.

The primary comparison of the proportion of subjects with allograft survival will be between the subjects randomized to placebo or C1-INH. It is anticipated that very few subjects will be lost to follow-up as standard of care mandates close follow up by the transplanting center. This endpoint will be analyzed after all subjects have been followed for 4 years after enrollment.

The power for hypothesis testing of this endpoint was estimated using the power procedure in SAS STAT under the following assumptions:

- The proportions of subjects with allografts surviving at 4 years after enrollment will be 0.25 with the placebo cohort and 0.75 in the C1-INH cohort.
- Alpha = 0.05 (two-sided test).

- Logistic regression model with treatment effect will be used for the primary efficacy analysis. Wald test statistic for treatment effect from Logistic regression has approximately same distribution as chi-square [[Fleiss et al, 2003](#)]. Therefore, the sample size calculation based on chi-square test is used to ensure similar power for hypothesis testing.
- Approximately 30 subjects in each randomized treatment groups.

There is greater than 90% power to detect the specified target difference between C1-INH and placebo groups based on sample size of 60 (approximately 30 in the C1-INH cohort and approximately 30 in the placebo cohort).

The 4-year graft survival for placebo of 25% is based on data presented at the American Transplant Congress in Boston [[Viglietti et al, 2016b](#)]. This study involved follow-up of kidney transplant recipients with biopsy-proven active AMR diagnosed between 2007 and 2013. Among the subjects who have not responded to standard of care, the 4-year graft survival ranged from approximately 10% to 40% for subjects with high and intermediate risk scores, respectively. The 4-year graft survival for C1-INH of 75% represents what would be expected for subjects who are successfully treated.

10.1.3 Sample Size Re-estimation

Data on which to estimate the effect size for the primary endpoint is limited. Because of the relatively high degree of uncertainty surrounding the true treatment effect, an unblinded sample size re-estimation is planned.

The interim analysis and sample size re-estimation will be performed by the independent Statistical Data Analysis Center supporting the IDMC. In order to maintain study integrity, the results of the interim analysis will not be revealed to CSL or otherwise made public. The sample size will not be reduced based on sample size re-estimation. The details of sample size re-estimation will be provided in an independent charter for IDMC. The recommendations from IDMC to CSL will be non-binding as a guideline to aid decision-making rather than a definitive rule.

10.2 Description of Study Analysis Sets

10.2.1 Screened Analysis Set

The Screened analysis set comprises all subjects who provided written informed consent and who undergo study screening procedures.

10.2.2 Enrolled Analysis Set

The Enrolled analysis set comprises all subjects in the Screened analysis set who do not fail screening.

10.2.3 Intent-to-Treat Analysis Set

The Intent-to-treat (ITT) analysis set comprises all subjects who were randomized. Subjects will be analyzed according to the investigational product to which they were assigned (ie, continued C1-INH or placebo) regardless of what was actually received. Any subject who receives a randomization identification number will be considered to have been randomized.

10.2.4 Modified Intent-to-Treat Analysis Set

All subjects randomized under the original protocol and under all protocol amendments will be included in this population except the subjects randomized prior to amendment 3 who do not satisfy the criteria in amendment 3. This modified ITT set will be the primary analysis set for the analysis of efficacy data.

10.2.5 Safety Analysis Sets

10.2.5.1 Run-in Safety Analysis Set

The Run-in Safety (RiS) analysis set will include all subjects who received at least one dose of C1-INH during TP1.

10.2.5.2 Randomized Withdrawal Safety Analysis Set

The Randomized Withdrawal Safety (RWS) analysis set will include all subjects in the ITT analysis set who received at least one dose of the investigational product after randomization during TP2. The RWS analysis set will be based on the investigational product actually received (ie, continued C1-INH or placebo) during TP2.

10.2.6 Pharmacokinetic Analysis Set

The PK analysis set will comprise all subjects who receive ≥ 1 dose of C1-INH and who have ≥ 1 measurable level of C1-esterase inhibitor functional activity or C1-esterase inhibitor antigen concentration.

10.2.7 CCI

CCI

10.3 Statistical Analyses and Methods

A complete description of the statistical analyses and methods will be available in a statistical analysis plan, which will be finalized before the database is locked.

Unless otherwise stated, efficacy analyses will be based on the modified ITT analysis set for analyses of endpoints defined in TP2. Sensitivity analyses will be based on the ITT set.

Enrolled analysis set will be used for the analysis of endpoints defined over the entire study. Sensitivity analyses of these endpoints will be done with ITT and modified ITT sets.

Safety will be summarized over the entire study, and according to treatment period. Safety will be analyzed for either the RiS analysis set or the RWS analysis set, as appropriate.

All data will be summarized in tables or figures and all ICH-required data in the database will be listed. Unless otherwise specified, continuous variables will be summarized by presenting the number of non-missing observations, mean, standard deviation, median, minimum and maximum. Other descriptive statistics (eg, 25th and 75th percentile, coefficient of variation) will be reported when appropriate. Categorical variables will be summarized by presenting the number of subjects and percentage for each category.

Unless otherwise stated, the statistical model on which inference is based will contain terms for the randomization strata as well as treatment. It is anticipated that subject accrual will be spread thinly across the centers. There will be no pooling of centers for purposes of analysis. Therefore, investigation of center-by-treatment interaction will not be possible.

Unless otherwise specified, all confidence intervals and *P*-values will be two-sided. From a formal inferential perspective, the type I error will be fully allocated to the analysis of the primary efficacy variable, and the selected secondary efficacy variable (ie, all-cause allograft failure after randomization into TP2 and through the Responder Follow-up Period). A serial gatekeeper hierarchical testing strategy will be used to protect the overall type I error rate of 0.050 (two-sided). Statistical significance will be claimed only when the results of the two-sided test favor C1-INH.

Supportive and secondary analyses will be inspected for consistency and directionality. *P*-values for supportive and/or secondary analyses will be used to provide guidance on the weight of evidence for any observed effects. *P*-values for supportive and/or secondary analyses will not be adjusted for multiplicity.

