2.2.2 Secondary Endpoints

Table 8 Secondary Endpoints

Secondary Objective	Endpoints	Summary Measure
1	All-cause allograft failure through the Responder Follow-up Period (key secondary).	Proportion of subjects with all-cause allograft failure through the Responder Follow-up Period (ie, within 48 months after enrollment). Allograft failure is defined as 1 of the following (see also Section 8.1.3.7): 
• Allograft nephrectomy, institution of permanent dialysis, or return to the transplant waitlist for renal transplant, whichever occurs first, OR• Subject death by any cause.
1	Change in eGFR from baseline to TP1	The difference between the End-of-TP1 eGFR and baseline eGFR.
1	Change in eGFR from TP1 to the End-of -TP2.	The difference between the End-of-TP2 eGFR and the End-of-TP1 eGFR.
1	The rate of change of eGFR.	The rate of change of eGFR during TP2 as defined by the slope of the mean regression of eGFR over time in TP2.
1	Time (weeks) to all-cause allograft failure through the Responder Follow-up Period (key secondary).	Time (weeks) to all-cause allograft failure through the Responder Follow-up Period (ie, within 48 months after enrollment).
1	Responder status at the End-of-TP1.	Proportion of responders at the End-of-TP1. Response is defined as End-of-TP1 eGFR that is ≥ 20 mL/min/1.73 m ² and $\geq 90\%$ of the baseline eGFR.
1	Subject death through the Responder Follow-up Period.	Proportion of subjects surviving through the Responder Follow-up Period.

Secondary Objective	Endpoints	Summary Measure
2	Any AE assessed as related to investigational product during TP1 and during TP2.	Proportion of subjects with any AE assessed as related to investigational product.
3	Pre-dose C1-esterase inhibitor functional activity at Day 1, Week 12, and Week 38.	Mean pre-dose C1-esterase inhibitor functional activity at Day 1, Week 12, and Week 38.
3	For the subset of subjects with sequential PK sampling, C1-esterase inhibitor functional activity C_{max} , and AUC_{0-t} after IV and/or SC administration of C1-INH.	C1-esterase inhibitor functional activity C_{max} and AUC_{0-t} for IV and SC administration.

AE = adverse event; AUC_{0-t} = area under the plasma-concentration time curve 0 to a definite time; C_{max} = maximum concentration; eGFR = estimated glomerular filtration rate; IV = intravenous; PK = pharmacokinetic; SC = subcutaneous; TP1 = Treatment Period 1; TP2 = Treatment Period 2

CSL Behring LLC

[figure not shown]
CSL842_3001

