10.3.3 Efficacy Analyses

All efficacy endpoints will be analyzed based on Modified-ITT analysis set. Sensitivity analyses for efficacy endpoints will be based on ITT set.

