10.3.3.2 Secondary Analyses

Analysis of key secondary endpoint of proportion of all-cause allograft failure at the end of 48 months after enrollment

The primary comparison for the proportion of subjects with all-cause allograft failure at the end of 48 months after enrollment will be based on a logistic regression model. The randomized treatment groups, C1-INH and placebo, will be compared based on the logistic model.

The same logistic model as described for the primary endpoint will also be used for this analysis.

Analysis of components of all-cause allograft failure after enrollment into TP1 through the Responder Follow-up Period (ie, within 48 months after enrollment) will be summarized for the randomized treatment groups and also the non-responder subjects who were not randomized in TP2. The summary will be based on the proportion of subjects with:

- Any event (ie, all-cause allograft failure or death by any cause).
- All-cause allograft failure (defined by allograft nephrectomy, or institution of permanent dialysis, or return to the transplant waitlist for renal transplant);
- Surviving allografts
- Death by any cause

Proportion of subjects with all cause allograft failure will be also summarized by treatment groups at 1 year, 2 years, and 3 years since enrollment.

Analysis of key secondary endpoint of time to all-cause allograft failure through 48 months after enrollment

Treatment group differences will be analyzed with a Cox proportional hazards regression model with randomization strata as covariates. This model will be used to estimate the C1-INH /placebo hazard ratio and two-sided 95% confidence interval. Kaplan-Meier plots of time to failure through the Responder Follow-up Period will be produced.

Subgroup analysis of loss-of-response at the End-of-TP2

Details of subgroup analyses will be provided in the SAP.

The following subgroups, and possibly others to be described in the SAP, will be summarized by treatment group with respect to the proportion of loss-of-response:

- Geographic region: USA, non-USA.
- DSA by randomization strata: sensitized, de novo.
- DSA by classification: HLA class I, HLA class II, both HLA class I and II.
- AMR severity: severe, non-severe (all other severities).
- Type of donor: deceased, living.
- Recipient race: Black, non-Black.
- Recipient sex: male, female.
- Recipient age: < 65 years, \geq 65 years.

Subgroup analysis of all-cause allograft failure at the end of 48 months after enrollment

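### The protocol's alpha-protected key secondary needs one analysis set, one endpoint and one meaning of all-cause allograft failure

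*Protocol*

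**What the plan says.** **Analysis set.** Protocol 10.3 states "Enrolled analysis set will be used for the analysis of endpoints defined over the entire study", with ITT and mITT as sensitivity sets. Protocol 10.3.3 states "All efficacy endpoints will be analyzed based on Modified-ITT analysis set", with ITT as sensitivity, and the synopsis agrees with it. By 10.2.2 the Enrolled set is everyone who passes screening, randomized or not.

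**Endpoint.** Protocol 10.3 states "A serial gatekeeper hierarchical testing strategy will be used to protect the overall type I error rate of 0.050 (two-sided"). It allocates alpha to the primary and to "the selected secondary efficacy variable (ie, all-cause allograft failure after randomization into TP2 and through the Responder Follow-up Period"). Table 8 gives the key label to the proportion with all-cause allograft failure and also to "Time (weeks) to all-cause allograft failure through the Responder Follow-up Period (key secondary"). Protocol 10.3.3.2 repeats both labels. The proportion gets the primary's logistic model, with treatment only; the time gets a Cox model with the randomization strata.

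**Death.** The synopsis, Table 8 and SAP 8.2.9 count death as all-cause allograft failure. The component list in 10.3.3.2 opens with "Any event (ie, all-cause allograft failure or death by any cause"). It then defines the same term by nephrectomy, permanent dialysis or return to the waitlist, and lists death on its own. The component lists for the primary endpoint (protocol 10.3.3.1, SAP 10.1) use the term in the same death-free way.

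**After termination.** SAP 4.2.1.3 and 7.3 drop formal testing. SAP 10.2 says the key secondary cannot be analyzed, and SAP 10.3 gives time to failure as a listing only.

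**The concern.** A test that carries part of the confirmatory type I error needs one population, one variable, one model and a place in the sequence. Here the general rule in 10.3 names a population that includes subjects without an arm, and it names the randomized sets only as sensitivity. Two endpoints with different models carry the key label, but there is one protected slot. The term that names the endpoint has two meanings. Had the trial run to 48 months, these choices could have been argued over after the data were seen.

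**Working it through.** **1. The plan's own figure.** Protocol 10.1.2 assumes that 4-year allograft survival "will be 0.25 with the placebo cohort and 0.75 in the C1-INH cohort", about 30 subjects per arm, and "Alpha = 0.05 (two-sided test"). It states power above 90%. In terms of failure this is 0.75 against 0.25.

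- Pooled normal approximation: the null SE is √(2 × 0.5 × 0.5 / 30) = 0.1291 and the alternative SE is √((0.75 × 0.25 + 0.25 × 0.75) / 30) = 0.1118. Power = Φ((0.50 − 1.96 × 0.1291) / 0.1118) = Φ(2.21) = 98.6%.
- Likelihood-ratio chi-square approximation: 97.7%.
- Logistic Wald test, exact enumeration over two binomials of 30, tables with an empty cell counted as not significant: 98.4%.

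The stated figure is reproduced. It belongs to the proportion, death included, in randomized subjects.

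**2. Analysis set.** Protocol 3.5 plans about 120 subjects (up to 175) in TP1 in order to randomize 60. Subjects without an arm: 120 − 60 = 60 (50%), up to 175 − 60 = 115 (66%). The synopsis, 10.1.2 and 10.3.3.2 all describe a comparison of the randomized groups, so the Enrolled set cannot be the set for that test.

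**3. Which endpoint.** Pointing to the proportion: the synopsis names a single key secondary, analyzed by logistic regression; 10.1.2 powers only the proportion; SAP 10.2 keeps the word key in its heading for the proportion, and SAP 10.3, on time to failure, does not. Pointing the other way: Table 8 and 10.3.3.2. No section orders the two or splits alpha. The gatekeeper sentence also counts from randomization, while Table 8 counts 48 months from enrollment.

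**4. Error if both forms were tested at 0.05.** The bound for two tests is 0.05 + 0.05 = 0.10, but both tests use the same events and are highly correlated. Simulation under no treatment difference: 20,000 trials, 30 per arm, exponential failure times, no dropout, and an unstratified log-rank test in place of the Cox model.

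| 48-month failure, both arms | Logistic Wald | Log-rank | Either |
|---|---|---|---|
| 25% | 0.0382 | 0.0493 | 0.0501 |
| 50% | 0.0471 | 0.0479 | 0.0554 |
| 75% | 0.0408 | 0.0538 | 0.0655 |

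The Monte Carlo standard error is about √(0.05 × 0.95 / 20,000) = 0.0015. The step is reached only if the primary is significant. If neither endpoint has an effect, the primary's 0.05 therefore still bounds the overall error.

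**5. The time form, if kept.** Under proportional hazards the planning rates imply HR = ln 0.75 / ln 0.25 = 0.208, with 30 × 0.75 + 30 × 0.25 = 30 expected events. Schoenfeld power = Φ(√30 / 2 × |ln 0.208| − 1.96) = 99.1%. A third step needs no more subjects.

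**6. What the death label could move.** The documents give no death rate. If 10%, 20% or 30% of failures in each arm were deaths with a working graft, excluding them would give exact Wald power of 95.6%, 90.1% or 81.5%. If instead 5, 10 or 15 percentage points were removed from each arm, it would be 98.4%, 98.0% or 94.9%.

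**The case against.** The best reply is that the intent can be recovered. Three places fix the comparison to randomized arms, and the gatekeeper's own variable is failure after randomization, which only randomized subjects can have. The Enrolled sentence has a sensible descriptive use, because 10.3.3.2 also summarizes the non-responders who were never randomized. The synopsis, 10.1.2 and SAP 10.2 point to the proportion, and 10.3 treats p-values for other secondary analyses as supportive only. A component table should show death on its own line. All of this stands, and it limits the point to wording. It does not remove it: the Enrolled rule in 10.3 has no exception for comparative endpoints, and nothing in the protocol withdraws the second key label.

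Three stronger readings are tempting, and the documents do not support them.

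- A reader might infer that non-responders would be counted in the C1-INH arm by drug received, which would dilute the effect. No section proposes this, and 10.3.3.2 reports them separately.
- A reader might infer that the sponsor could freely claim success on either of two tests. That means disregarding the synopsis, 10.1.2 and the supportive status of other secondary analyses. Even then the excess error is small and sits behind the primary.
- A reader might infer that the tested endpoint excludes death. Its definition in the synopsis, Table 8 and SAP 8.2.9 includes death; the death-free use is in the component lists.

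**Conclusion.** The point holds as a defect of definition in the protocol. The set rule in 10.3 conflicts with the synopsis and 10.3.3, and it cannot serve the planned comparison, because 50% to 66% of the Enrolled set would have no arm. Two endpoints share the key label, with one protected slot and no order. One term has two meanings.

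The size is modest. Error at that step would be about 5.0% to 6.6% instead of 5%, under assumed exponential times and full follow-up, and only once the primary had succeeded. On the protocol's planning rates the stated power above 90% holds for the best-supported version (about 98%).

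The trial stopped with 13 subjects randomized, and the SAP plans no formal test and no analysis of this endpoint. No reported inference is affected; the correction is to the protocol. The one trace in a planned output is the component label in SAP 10.1.

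**What to change.** - **Protocol 10.3:** limit the Enrolled sentence to non-comparative summaries, such as the TP1 responder proportion and descriptive tables that include non-responders. State that every comparison of randomized groups uses mITT, with ITT as sensitivity.
- **Protocol 10.3, Table 8 and 10.3.3.2:** name the proportion with all-cause allograft failure within 48 months after enrollment, death included, logistic Wald test, as step 2 of the hierarchy. Make time to failure (Cox) step 3, or remove its key label.
- **Protocol 10.3.3.1 and 10.3.3.2, and SAP 10.1:** rename the death-free component *allograft failure*, as 8.1.3.7 already does. For consistency, the definitions in the synopsis and Table 8 that include death should then read *all-cause* allograft failure.

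The cost is wording only: no added data, subjects or analyses, and the power statement in 10.1.2 can stay as it is.
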